4. CODING SYSTEMS UTILIZED

All variables were coded to create the primary efficacy analysis.

| AGE | Age of patients |
|-------|----------------------------|
| COMP1 | Composite score at Day 100 |

Cerebrolysin and repetitive Transcranial Magnetic Stimulation (rTMS) in patients with Traumatic Brain Injury

Version 1.0

| COMP2 | Composite score at Day 180 |
|-------------------|--|
| CWTTM1_1 | Stroop Color Word Test – Word Task - Number of seconds at Visit 1 - Baseline |
| CWTTM1_2 | Stroop Color Word Test – Word Task - Number of seconds at Visit 2 – Day 100 |
| CWTTM1_3 | Stroop Color Word Test – Word Task - Number of seconds at Visit 3 – Day 180 |
| CWTTM2_1 | Stroop Color Word Test – ColorTask - Number of seconds at Visit 1 - Baseline |
| CWTTM2_2 | Stroop Color Word Test – Color Task - Number of seconds at Visit 2 – Day 100 |
| CWTTM2_3 | Stroop Color Word Test – Color Task - Number of seconds at Visit 3 – Day 180 |
| CWTTM3_1 | Stroop Color Word Test – Color-Word Task - Number of seconds at Visit 1 - Baseline |
| CWTTM3_2 | Stroop Color Word Test – Color-Word Task - Number of seconds at Visit 2 – Day 100 |
| CWTTM3_3 | Stroop Color Word Test – Color-Word Task - Number of seconds at Visit 3 – Day 180 |
| DGBRES_1 | Digit Span – Digit Backward Total Score at Visit 1 - Baseline |
| DGBRES_2 | Digit Span – Digit Backward Total Score at Visit 2 – Day 100 |
| DGBRES_3 | Digit Span – Digit Backward Total Score at Visit 3 – Day 180 |
| DGFRES_1 | Digit Span – Digit Forward Total Score at Visit 1 - Baseline |
| DGFRES_2 | Digit Span – Digit Forward Total Score at Visit 2 – Day 100 |
| DGFRES_3 | Digit Span – Digit Forward Total Score at Visit 3 – Day 180 |
| DS_B_v1-baseline | Digit Span Backward Baseline Difference Day 100 |
| DS_B_v2-baseline | Digit Span Backward Baseline Difference Day 180 |
| DS_F_v1-baseline | Digit Span Forward Baseline Difference Day 100 |
| DS_F_v2-baseline | Digit Span Forward Baseline Difference Day 180 |
| D_PRESDT_VISDTC_2 | D_PRESDT_VISDTC_2 |
| D_PRESDT_VISDTC_3 | D_PRESDT_VISDTC_3 |
| GROUP | GROUP |
| HADS_v1-baseline | Hamilton Anxiety Rating Scale Baseline Difference Day 100 |
| HADS_v2-baseline | Hamilton Anxiety Rating Scale Baseline Difference Day 180 |
| HARTS_1 | Hamilton Anxiety Rating Scale - Total score at Visit 1 - Baseline |
| HARTS_2 | Hamilton Anxiety Rating Scale - Total score at Visit 2 – Day 100 |
| HARTS_3 | Hamilton Anxiety Rating Scale - Total score at Visit 3 – Day 180 |

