7. STUDY SCHEDULE

Screening and Baseline Visit – within 30 days of onset of TBI (Study Day 30+/- 4 days)

- Neurological and physical exam
- Hematology and blood chemistry
- Demographic data
- Medical history
- Concomitant Medication
- Evaluation Scales

Cerebrolysin and repetitive Transcranial Magnetic Stimulation (rTMS) in patients with Traumatic Brain Injury

Version 1.0

- Processing Speed Index
- Stroop Color-Word Test
- Trail Making Test
- o Digit Span
- Montreal Cognitive Assessment
- Hamilton Anxiety Rating Scale
- Hamilton Rating Scale for Depression
- One Touch Stockings of Cambridge
- o Multitasking Test
- Reaction Time
- ET
- qEEG

Visit 1 – Efficacy Evaluation (study day 101+/- 7days)

- Neurological and physical exam
- Evaluation Scales
 - Processing Speed Index
 - Stroop Color-Word Test
 - o Trail Making Test
 - o Digit Span
 - Montreal Cognitive Assessment
 - o Hamilton Anxiety Rating Scale
 - Hamilton Rating Scale for Depression
 - One Touch Stockings of Cambridge
 - Multitasking Test
 - Reaction Time
- ET
- qEEG

Visit 2 – Efficacy Evaluation (study day 180+/- 4 days)

- Neurological and physical exam
- Evaluation Scales
 - Processing Speed Index
 - Stroop Color-Word Test
 - Trail Making Test
 - o Digit Span
 - Montreal Cognitive Assessment
 - o Hamilton Anxiety Rating Scale
 - Hamilton Rating Scale for Depression
 - One Touch Stockings of Cambridge
 - o Multitasking Test
 - Reaction Time
- ET

Cerebrolysin and repetitive Transcranial Magnetic Version 1.0 Stimulation (rTMS) in patients with Traumatic Brain Injury

• qEEG

Treatment cycles:

- Study days 31-40,
- Study days 61-70
- Study days 91-100

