13.3. Treatment Compliance

Each patient will receive three cycles of treatment of 10 infusions on 10 consecutive days:

- Study days 31-40,
- Study days 61-70
- Study days 91-100

Patients with compliance for the entire study below 80% for the treatments will be considered protocol violators and will not be included in the per protocol analysis.

Study Title

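### The SAP's symmetric Visit 1 window (day 101 ± 7) overlaps treatment cycle 3, so an in-window 3-month assessment can be made before treatment is complete; the baseline window also conflicts with the schedule

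*SAP*

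**What the plan says.** SAP section 7 (Study Schedule) gives three visit windows:

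- baseline: "Screening and Baseline Visit – within 30 days of onset of TBI (Study Day 30+/- 4 days"
- 3-month assessment: "Visit 1 – Efficacy Evaluation (study day 101+/- 7days"
- 6-month assessment: "Visit 2 – Efficacy Evaluation (study day 180+/- 4 days"

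The same section lists treatment from "Study days 31-40" to "Study days 91-100", with a middle cycle on days 61 to 70. SAP section 13.3 adds: "Each patient will receive three cycles of treatment of 10 infusions on 10 consecutive days". That makes 30 infusions. SAP section 4 labels the 3-month data with phrases such as "Composite score at Day 100".

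Protocol section 11.1 has the same three visits without windows: baseline on study day 0, Visit 1 on day 101 (listed after the treatment cycles) and Visit 2 on day 180. Protocol section 7.1.1 counts each cycle in working days and gives the first cycle as days 32 to 40. Protocol section 11.1 and the SAP give days 31 to 40.

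The efficacy ensemble (protocol section 13.4.2, SAP section 9) consists of changes from baseline on nine scales, combined over 3 and 6 months.

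**The concern.** A window that is symmetric about day 101 reaches back into the cycle that ends on day 100. No SAP rule requires Visit 1 to follow the patient's last session. A 3-month assessment can therefore be fully in window while part of the course is still to be given. For that patient the change score does not describe the effect of the completed course, which is what the protocol's order of events implies.

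At stake is the meaning of one of the two time points in the primary comparison of rTMS plus Cerebrolysin with Cerebrolysin alone. If benefit accumulates over sessions, the contrast at that time point is diluted in a trial planned for only 80% power.

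The baseline window raises a related problem. Its upper end passes both the listed start of cycle 1 and the 30-day limit in its own line, so the SAP does not say unambiguously when baseline ends and treatment begins.

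**Working it through.** The documents state no overlap figure, so there is none to reproduce.

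**1. Day counts** (SAP section 7; one session per listed treatment day)

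| Visit | Window | Treatment days inside | Sessions on earlier days |
|---|---|---|---|
| Baseline | 30 ± 4 = 26–34 | 31–34 (4 of 9 days) | 0 on day 31; 3 on day 34 |
| Visit 1 | 101 ± 7 = 94–108 | 94–100 (7 of 15 days) | 23 on day 94; 29 on day 100 |
| Visit 2 | 180 ± 4 = 176–184 | none | 30 |

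For day 94: 10 + 10 + 3 (days 91–93) = 23. If testing precedes that day's session, 30 − 23 = 7 sessions remain. The protocol's nominal days 0, 101 and 180 do not fall on listed treatment days, so this overlap comes from the SAP windows.

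**2. Can a baseline really be on treatment?** SAP section 7 treats screening and baseline as one visit. SAP section 6.3 gives a random number only to patients who already meet the entry criteria. A patient first seen on day 34 should therefore not have been treated on days 31 to 33. The line also says "within 30 days of onset of TBI (Study Day 30+/- 4 days". If study days count from injury, days 31 to 34 break the first half of that line. The origin is itself unsettled, because the protocol calls baseline day 0. These statements contradict each other; they do not establish a treated baseline.

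**3. Does another reading of the schedule remove the Visit 1 problem?**

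- *Cycles move with a late baseline* (assumed to start the next day): a baseline on days 31 to 34 shifts the end of cycle 3 to days 101 to 104.
- *Ten working days* (Monday to Friday assumed): a cycle spans 12 to 14 calendar days, so one starting on day 91 ends on days 102 to 104.

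In both cases even nominal day 101 can fall inside treatment. A fixed-day window secures a post-treatment Visit 1 under neither reading.

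**4. Illustrative size.** From protocol section 13.9: d = 0.5, ρ = 0.4, one-sided α = 0.05, and 30 per arm including a 10% allowance, taken here as n = 27 evaluable. Nine scales, from section 13.4.2. Assumptions not in the documents: the effect is proportional to sessions completed, baseline is untreated, and the full effect is present at Visit 2.

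- MW = Φ(d/√2).
- SE² = (2n+1)/(12n²) × (1 + 8ρ)/9 = 55/8748 × 4.2/9 = 0.00293, so SE = 0.0542.
- Power = Φ((average MW − 0.5)/SE − 1.645), averaging MW over the two visits.

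| Visit 1 timing | Mean sessions | Visit 1 d | Visit 1 MW | Average MW | Power |
|---|---|---|---|---|---|
| After the last session | 30 | 0.500 | 0.638 | 0.638 | 82% |
| Spread evenly, days 94–108 | 422/15 = 28.13 | 0.469 | 0.630 | 0.634 | 80% |
| Every patient on day 94 | 23 | 0.383 | 0.607 | 0.622 | 73% |

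The sum 422 is (23 + … + 29) + 8 × 30 = 182 + 240. With a variance for 18 components (nine scales at two visits, all at ρ = 0.4), the factor becomes (1 + 17 × 0.4)/18 = 0.433 and the first two powers become 84% and 82%. The calculation follows the protocol's multivariate Wilcoxon-type test.

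**The case against.** The strongest reply is that the practical effect is small and its direction is not certain. With dates spread evenly the loss is about 2 percentage points, and with the 18-component variance power stays above 80%. The 73% needs every patient to be seen on the earliest permitted day. Linear accrual has no support in the documents; a test made during treatment could also pick up a transient effect and enlarge the contrast. The windows are identical in all arms and assessment is blinded, so no differential bias is shown. All of this stands, and it argues against treating the point as critical.

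Protocol section 11.1 also places Visit 1 after the cycles, and protocol section 13.13.1 provides a blind review of protocol violations. The SAP's variable list includes items whose names suggest that differences from planned visit dates are held. But these items are undefined, and none of this amounts to a rule that a visit inside cycle 3 is out of window. The SAP wording still permits it.

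A reader might go further and infer three things that the documents do not support:

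- *That both ends of the change score can be measured mid-treatment.* The order of screening and randomisation speaks against a treated baseline, and the Visit 2 window is clear of treatment.
- *That the SAP classes these visits as compliant.* Its compliance rule (section 13.3) concerns the share of treatment received, not visit timing.
- *That the "Composite score at Day 100" labels show testing on a treatment day.* They are nominal labels, and section 7 gives day 101.

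**Conclusion.** The Visit 1 point holds: 7 of 15 in-window days are listed treatment days, and up to 7 of 30 scheduled sessions can still be outstanding at an in-window 3-month assessment. This is exact arithmetic on the SAP's own figures and needs no assumption about effect.

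The baseline point holds only as an inconsistency. The study-day origin (0 or 30), the 30-day limit, the ± 4 window and the start of cycle 1 cannot all be applied as written. It is not proof that any baseline was taken on treatment.

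The consequence for power (about 82% to about 80%, or about 73% at the extreme) is illustrative. It rests on linear accrual by session, an untreated baseline, 27 per arm and nine scales at a common correlation of 0.4. The documents do not give actual visit dates, so the real effect cannot be computed. This should be fixed, but it does not by itself put the trial's conclusion in doubt.

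**What to change.** In SAP section 7, define the windows by actual dates:

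- Baseline tests count as baseline only if completed before the patient's first infusion or rTMS/sham session.
- Visit 1 is in window only if held after the patient's last cycle-3 session, for example 0/+7 days from the planned post-treatment day. State separately how the window is set for a patient who does not reach or complete cycle 3, so that nobody leaves the ITT analysis through this rule.
- Add a sensitivity analysis of the primary comparison without Visit 1 assessments already held inside a cycle, and report their number by arm.
- Define the SAP's visit-date difference variables against these dates, and align the day labels in section 4 with section 7.

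Separately, reconcile protocol sections 7.1.1 and 11.1 with SAP sections 7 and 13.3 on the study-day origin, calendar or working days, and the first day of cycle 1. Which schedule is right is for the sponsor and the investigator to settle; the date-based windows work under any of them and change no treatment.

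The cost is a few lines of SAP text, a note to the site, one additional analysis, and slightly less scheduling freedom before day 101. Visit dates are already among the SAP variables, and protocol section 11.2 records the date and time of each administration in the CRF.

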8. STUDY ENDPOINTS

8.1. Primary Endpoints

- Processing Speed Index
- Stroop Color-Word Test
- Trail Making Test
- Digit Span
- Montreal Cognitive Assessment
- One Touch Stockings of Cambridge (CANTAB)
- Reaction Time (CANTAB)
- Multitasking Test (CANTAB)
- Hamilton Rating Scale for Depression
- Hamilton Anxiety Rating Scale

8.2. Secondary Endpoints

- Eye tracking parameters
- Quantitative EEG parameters
- rTMS adverse events

8.2.1. Efficacy

An ensemble of appropriate single efficacy criteria shall be tested by a multivariate, directional test approach, reflecting the "global status of patients in TBI" (Bagiella, 2010), while simultaneously combining two points in time in the sense of a 'repeated measures design'.

The following ensemble of appropriate single efficacy criteria shall be tested by a multivariate, directional test approach, reflecting the global status of patients in TBI after 3 and 6 months:

Multivariate Efficacy Ensemble

- 1. Processing Speed Index, Changes from Baseline, LPCF, ITT
- 2. Stroop Color-Word Test, Changes from Baseline, LPCF, ITT
- 3. Trail Making Test, Changes from Baseline, LPCF, ITT

Cerebrolysin and repetitive Transcranial Magnetic Stimulation (rTMS) in patients with Traumatic Brain Injury

Version 1.0

- 4. Digit Span, Changes from Baseline, LPCF, ITT
- 5. Montreal Cognitive Assessment, Changes from Baseline, LPCF, ITT
- 6. Stockings of Cambridge (CANTAB), Changes from Baseline, LPCF, ITT
- 7. Reaction Time (CANTAB), Changes from Baseline, LPCF, ITT
- 8 Hamilton Rating Scale for Depression, Changes from Baseline, LPCF, ITT
- 9. Hamilton Anxiety Rating Scale, Changes from Baseline, LPCF, ITT

8.2.2. Safety

A Serious/Adverse Event (S/AE) is any untoward medical occurrence in a patient or clinical investigation subject administered a pharmaceutical product and which does not necessarily have a causal relationship with this treatment. An AE can therefore be any unfavourable and unintended sign (including an abnormal laboratory finding), symptom, or disease temporally associated with the use of an Investigational Product, whether or not related.

Adverse Drug Reactions (ADR) are all untoward and unintended responses to an Investigational Product related to any application / dose administered. The phrase "responses to an Investigational Product" means having a reasonable causal relationship as judged by either the Investigator or the Sponsor. The expression reasonable means to convey in general that there is evidence or argument to suggest a causal relationship. Regarding marketed Investigational Products: a response to a product which is noxious and unintended and which occurs at applications normally used in man for prophylaxis, diagnosis, or therapy of diseases or for modification of physiological function.

Serious Adverse Events will due to the underlying constitution of the patient be considered for AE documentation. Serious Adverse Drug Reactions will be dealt with as described below.

Expedited Reporting is required if the following criteria apply (ICH E2A):

- 1. Serious
- 2. Unexpected
- 3. Reasonable causal relationship to study treatment.

An Adverse Drug Reaction is considered serious if it:

- Results in Death
- Is life threatening
- Requires additional inpatient hospitalization or prolongation of existing hospitalization
- Results in persistent or significant disability / incapacity
- Results in a congenital anomaly or birth defect

Cerebrolysin and repetitive Transcranial Magnetic Version 1.0 Stimulation (rTMS) in patients with Traumatic Brain Injury

• Other medically significant event that requires immediate medical or surgical intervention

Unexpected means:

• Not consistent with Investigators Brochure or SmPC

Causal Relationship means:

- There are facts/evidence to suggest a causal relationship
- As judged by the reporting health care professional to have reasonable suspected causal relationship

All adverse events, according to previously provided definitions, whether they are considered serious or not will be documented and were applicable reported. The Investigator must report in detail all adverse signs and symptoms which are either volunteered by patients or observed during or following the course of Investigational Product administration on the appropriate CRF page. Included in the description should be the nature of the sign or symptom; the date of onset; date of resolution (duration); the severity / intensity; the relationship to study treatment or other therapy; the action taken (if any), and the outcome.

All Serious Adverse Reactions and all Unexpected Serious/Adverse Reactions with at least a suspicion of causal relationship to the investigational product must be reported to the Sponsor within 24 hours (one working day) of the Investigator knowing. Preference in the reporting is the SAE report by e-mail.

Cerebrolysin and repetitive Transcranial Magnetic Stimulation (rTMS) in patients with Traumatic Brain Injury

9. SPECIFICATIONS OF EFFICACY CRITERIA

Multivariate Efficacy Ensemble

- 1. Processing Speed Index, Changes from Baseline, LPCF, ITT
- 2. Stroop Color-Word Test, Changes from Baseline, LPCF, ITT
- 3. Trail Making Test, Changes from Baseline, LPCF, ITT
- 4. Digit Span, Changes from Baseline, LPCF, ITT
- 5. Montreal Cognitive Assessment, Changes from Baseline, LPCF, ITT
- 6. Stockings of Cambridge (CANTAB), Changes from Baseline, LPCF, ITT
- 7. Reaction Time (CANTAB), Changes from Baseline, LPCF, ITT
- 8 Hamilton Rating Scale for Depression, Changes from Baseline, LPCF, ITT
- 9. Hamilton Anxiety Rating Scale, Changes from Baseline, LPCF, ITT

This ensemble of appropriate single efficacy criteria shall be tested by a multivariate, directional test approach, reflecting the global status of patients in TBI after 3 and 6 months.

All efficacy criteria will be analyze with descriptive group statistics.

10. ANALYSIS SETS

ITT population will be used for all efficacy analyses. ITT population is defined as all patients who have no "severe" violation of entry criteria, had at least one dose of medication and at least one post-baseline observation of at least one primary efficacy criterion ("modified" ITT). This way ITT is defined in the sense of the "full analysis set" according to ICH E9 § 5.2. ("Analysis Sets").

A sensitivity analysis will be performed for a per protocol (PP) data set as an exploratory approach. The PP population includes all patients who are eligible for ITT evaluation and who additionally do not show major protocol deviations. The supportive analysis by means of the per-protocol set will be regarded as of equal scientific importance as the ITT analysis, since it most closely reflects the scientific model underlying the protocol (see ICH E9, section 5.2.2).

Safety population includes all patients who have had at least one dose of study medication and one contact with the Investigator afterwards. It will be used for safety analysis.

11. DATA REVIEW

Any data to be recorded directly into the CRFs will be identified at the start of the study. The investigator will ensure the accuracy, completeness legibility and timeliness of data reported in the CRF and all required reports. Any change or correction to a paper CRF must be dated, initialled and explained (in case of an eCRF data entries are already monitored by an audit trail) and must not obscure the original entry, this applies to both written and electronic

Cerebrolysin and repetitive Transcranial Magnetic Stimulation (rTMS) in patients with Traumatic Brain Injury

Version 1.0

changes.

On termination of the study, the study documents, including the emergency envelopes are to be returned to the Coordinator. These records are to be retained for the periods required by ICH-GCP, i. e. until at least 2 years after the last approval of a marketing application in an ICH region and until there are no pending or contemplated marketing applications in an ICH region or at least 2 years have elapsed since the formal discontinuation of clinical development of the Investigational Product (CPMP/ICH/135/95), or by national legal requirements, whichever is longer, but not less than 15 years after routine/premature termination of a clinical study. The final report shall be retained for at least 2 years after the Investigational Products are removed from the last market. The informed consent forms and all the original (raw) data are to be retained by the head of the clinical study or the investigating physicians for at least 15 years.

The responsibilities of the Investigator, Monitor and Coordinator of the clinical study as regards handling of data, storage of data, planning, assessment and quality assurance are regulated by the recommendations on "Good Clinical Practice" of the "International Conference on Harmonisation" (ICH) and apply to this clinical study.

The Investigator will permit study-related monitoring, audits, IRB / IEC review and regulatory inspections, providing direct access to primary patient data (i.e. source data) which supports the data on the CRFs for the study, i.e. general practice charts, appointment books, original laboratory records etc. Authorized, qualified Clinical Trial Monitor will visit the investigational site in regular intervals established based on the needs of the project, to verify adherence to protocol and local legal requirements, to perform source data verification and to assist the Investigator in his study related activities.

12. STATISTICAL METHODOLOGY

12.1. Data Handling

In order to identify each type of missing data, outcome scales will be coded for every patient and visit according to the following scheme (see also Bagiella, 2010):

- 1 = valid (complete task)
- 2 = unable to complete (TBI-related neurological reason) [describe reason]
- 3 = not completed (different reasons, not TBI related) [describe reason]

12.2. Descriptive Statistics

Descriptive account of all variables (raw and baseline difference)

- Range
- Minimum value
- Maximum value
- Mean (+ Std. error)

Cerebrolysin and repetitive Transcranial Magnetic Stimulation (rTMS) in patients with Traumatic Brain Injury

- Standard Deviation
- Variance
- Skewness (+ Std. error)
- Kurtosis (+ Std. error)

12.2 Confirmatory Statistics

Although this study is intended to be of exploratory nature, the analysis will be based on 'confirmatory' principles with pre-specification of the primary analyses and control of multiple level alpha.

Mean, median and distribution group difference hypotheses

• Kruskal-Wallis with Dunn's test.

Kruskal-Wallis Rank Sum Test will be used to assess the statistical significance of the differences across groups. The pairwise comparisons will be performed using Dunn's Kruskal-Wallis Multiple Comparisons, with the Bonferroni adjustment.

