13.7. Level of Significance

The multiple level alpha is set to α = 0.05, one-sided, according to current recommendations for randomized phase II trials (Rubinstein 2009; Sumithra 2010; Manish 2011).

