13.8. Multiplicity

Multiplicity regarding multiple primary outcome measures at two points in time is controlled by the chosen correlation-sensitive, multivariate test procedure (Wei-Lachin procedure, see also section 13.10).

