13.9. Sample Size Calculation

The power for this study is determined based on the following design specifications:

- (a) One-sided type I error defined as alpha = 0.05 (multiple level alpha, see section 13.7)
- (b) Type II error defined as $\beta = 0.2$ (Testpower 80%)
- (c) Design alternative effect size: Mann-Whitney statistic (MW) = 0.64 (medium-sized difference according to Cohen (Colditz, 1988); assuming a normal distribution the effect size MW may easily be re-expressed as the well-known Cohen effect size (Cohen, 1988) of a standardized difference (Cohen's d): MW = 0.64 means Cohen's d = 0.5)
- (d) Estimated correlations among the single outcome scales included in the global statistics $\rho = 0.4$)

Nonparametric sample size calculations within the framework of a multiple outcome approach (Wei-Lachin procedure- Wei and Lachin, 1984; Lachin 1992) was performed applying the validated software Nnpar 1.0 from idv Data Analysis and Study Planning, Krailling/Munich (see also Tang, 1989; Lachin, 1981). A good example for sample size calculation according to the Lachin approach (Wei and Lachin, 1984; Lachin 1992; Lachin, 1981) in multidimensional trials with neuroprotective agents is also given by Huang (2008).

Please note: further details of the effect size (Mann-Whitney statistic) are described in section 13.10, further details of sample size assessment are described in the separate document "Sample Size Assessment Based on a Multidimensional Efficacy Approach".

Based on the above design specifications, the total required sample size for the multivariate ensemble results in 30 patients per group (including 10% enhancement for usual "ambiguities", e.g., dropouts). With this sample size a "medium-sized" group difference (MW = 0.64) with regard to the multivariate outcome ensemble at month 3 and 6 can be detected with a power of 80%.

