13.10. Confirmatory Analyses

Minimizing the required assumptions is a recommended approach for confirmatory statements on efficacy (LaVange, 2005). This applies especially in scales with skewed distributions including floor and ceiling effects as is known from many scales used in TBI. Furthermore, data types can be of different nature (binary, ordinal, continuous). Thus, a non-parametric assessment of treatment effects independent of data type and distribution should be chosen as the primary analysis method.

The analysis will be performed using the Wei-Lachin procedure, a multivariate generalization of the Wilcoxon-Mann-Whitney test, which takes account of the correlation among univariate Mann-Whitney tests for each outcome to produce an overall average estimate of benefit and test for treatment differences. The summarizing test used is, however, not the undirectional or omnibus test of the classical procedure, but instead a directional test which is most efficient in the case of known direction for superiority.

The procedure is described by Wei and Lachin (1984) and Lachin (1992). Practical examples are given in modern textbooks on multiple testing problems(see e.g., Dimitrenko, 2010). Incidentally it should be noted that the nonparametric Wei-Lachin procedure is similar to the frequently used parametric procedure of O'Brien (O'Brien,

Date: 040418

1984). We prefer, however, the Wei-Lachin procedure as it is more robust for practical data sets (minimization of required assumptions (LaVange 2005)) and because the O'Brien procedure has been shown to give too liberal results (Frick 1997).

It is important to note, that the multivariate, directional test procedure chosen for this study can cope simultaneously with binary, ordinal and continuous data. Thus, there is no technical need for the widely used dichotomization of original scales which is associated with substantial loss of information and reflects a major disadvantage of previous TBI studies.

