13.4. ANALYSIS OF EFFICACY

Descriptive statistics and graphs will be generated for the ITT population. In addition, nonparametric effect sizes and confidence intervals (Kruskal Wallis and Dunn's pot hoc test) will be provided for all primary and secondary efficacy criteria at all points in time.

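### SAP 12.2 omits the protocol's primary Wei-Lachin test and names only Kruskal-Wallis with Dunn-Bonferroni, a method to which the stated 80% power and 5% error rate do not belong

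*SAP*

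**What the plan says.** Protocol 13.10 fixes the primary method: "The analysis will be performed using the Wei-Lachin procedure, a multivariate generalization of the Wilcoxon-Mann-Whitney test", used in its directional form. Protocol 13.4.1 combines two time points in it, and 13.4.2 lists nine change scores. Protocol 13.7 sets the level: "The multiple level alpha is set to α = 0.05, one-sided". Protocol 13.8 says that multiplicity over outcomes and time points "is controlled by the chosen correlation-sensitive, multivariate test procedure". Protocol 13.9 sizes the trial on the same test: a medium difference "with regard to the multivariate outcome ensemble at month 3 and 6 can be detected with a power of 80" per cent.

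SAP 12.2 (Confirmatory Statistics) commits to prespecified primary analyses and control of the multiple alpha. It then names only one method: "Kruskal-Wallis Rank Sum Test will be used to assess the statistical significance of the differences across groups", with Dunn's pairwise comparisons and Bonferroni. SAP 13.4 promises "nonparametric effect sizes and confidence intervals (Kruskal Wallis and" Dunn's post hoc test for every primary and secondary criterion at every time point. Protocol 13.10 and 13.11 specify the Mann-Whitney statistic with its confidence interval for that purpose.

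SAP 9 nevertheless says: "This ensemble of appropriate single efficacy criteria shall be tested by a multivariate, directional test approach", and SAP 8.2.1 says the same. The SAP does not mention Wei-Lachin. It gives no numerical alpha or sidedness and no rule across scales or visits. It repeats 30 per arm in 6.2. Its coding list (section 4) contains composites COMP1 and COMP2, without a formula or a stated role.

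**The concern.** Kruskal-Wallis with Dunn's test is univariate, and its omnibus stage has no direction, so it cannot be the test described in SAP 8.2.1 and 9. It also differs from the protocol's test in three ways that matter here:

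- Dunn's statistic ranks all three arms together, so the placebo arm affects the rTMS + CRB versus CRB comparison.
- Bonferroni spends alpha on three pairs, although only one is primary.
- Nothing in it handles multiplicity across scales and visits.

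Kruskal-Wallis and Dunn's test give test statistics and P-values. They do not give the effect sizes and intervals that SAP 13.4 expects from them.

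At stake is whether the primary question has one prespecified answer. Two analysts following this SAP could choose different scales, visits or composites and reach opposite conclusions, with neither departing from its text.

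**Working it through.** **Inputs.** From protocol 13.7 and 13.9: one-sided alpha 0.05, power 80%, MW 0.64 (d = 0.507 under normality; the protocol rounds to 0.5), correlation 0.4, and 30 per arm including a 10% allowance, so about 27 evaluable. Protocol 13.9 does not state the number of components K. Nine scales give K = 9, and two visits give K = 18.

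**1. The plan's own figure.** Noether's formula for one scale gives n per arm = (1.645 + 0.842)² / (12 × 0.25 × 0.14²) / 2 = 52.6. Averaging K components multiplies this by f = (1 + (K − 1) × 0.4)/K.
- K = 9: f = 0.467, n = 24.5, so 25; with 10% added, 28.
- K = 18: f = 0.433, n = 22.8, so 23; with 10% added, 26.

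The plan's 30 is close to the first result and on the safe side.

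**2. Power of the protocol's test.** Power = Φ(0.14/(SE × √f) − 1.645), with SE = √((2n + 1)/(12n²)) = 0.0793 at n = 27 and 0.0752 at n = 30.
- K = 9, n = 27: 0.14/(0.0793 × 0.683) − 1.645 = 0.94, so 83%.
- K = 18, n = 30: 0.14/(0.0752 × 0.658) − 1.645 = 1.18, so 88%.

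Simulation of the 18-component test under the global null gave a 5.0% error rate. The protocol's two figures hold for this test.

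**3. One scale, plain one-sided Mann-Whitney at 0.05.** Φ(0.14/SE − 1.645) = 55% (n = 27) to 59% (n = 30). This is the cost of leaving the ensemble, before any Dunn-Bonferroni adjustment.

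**4. One scale, Dunn-Bonferroni.** The SAP gives no alpha or sidedness, so two readings are shown:
- (a) Two-sided 0.05 over three pairs: 0.05/6 per direction, z = 2.394.
- (b) One-sided 0.05 over three pairs: 0.05/3, z = 2.128.

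With placebo equal to CRB, 0.14/SE is 1.77 (n = 27) or 1.86 (n = 30). Reading (a) gives about 26–30% and (b) about 36–40%. With placebo about 0.5 SD below CRB, the pooled ranks lower these figures by 3 to 4 points at a given n.

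**5. Simulated ranges.** Three normal arms, 27–30 per arm, equal effect and correlation 0.4 throughout, placebo from equal to CRB to about 0.5 SD below it, composite taken as a simple mean. Error rates are under the global null at 30 per arm and count only false results favouring rTMS + CRB over CRB.

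| Reading of the SAP | (a) 0.05/6 | (b) 0.05/3 |
|---|---|---|
| One scale, one visit: power | 23–30% | 32–40% |
| Mean composite, one visit: power | 48–63% | 60–74% |
| Either of two visit composites: power | 57–72% | 69–80% |
| Either of two visit composites: error | about 1% | at most 3.3% (2 × 0.05/3) |
| Any of 18 scale-visits: error | about 10% | about 17% |
| Any of 34 coded change scores: error | 14–15% | about 25% |

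The 34 are the 17 change variables in SAP section 4 at two visits. Under (a), power for any of 18 is 83–89%, but its error rate is about 10%.

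**6. Sensitivity to correlation.** At 0.2 (n = 30, placebo equal to CRB, reading (a)), per-visit composite power rises to 85%. At 0.6 it falls to 46%. The protocol assumes 0.4.

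**The case against.** **The SAP does not say it replaces anything.** Sections 8.2.1 and 9 keep the multivariate, directional wording, and no sentence states that Kruskal-Wallis supersedes protocol 13.10. This stands. The documents show an omission and a self-contradiction, not a declared change of method.

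**A reader might infer that power has fallen to about a third of what was promised.** The documents do not support that. The 80% was for the ensemble, never for a single scale. Even a plain one-sided Mann-Whitney test on one scale has only 55–59%, so part of the gap comes from leaving the ensemble.

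**A reader might also infer that false positives are simply uncontrolled.** That requires a rule that any one significant scale counts as success, which the SAP does not state. If COMP1 and COMP2 were meant, the false favourable rate would be about 1% under reading (a), which is conservative. Protocol 4.1 calls the outcomes co-primary; requiring all 18 tests to succeed would also be conservative, but simulated power under (a) is then below 1%. Error counts over every pair in either direction would look worse, but they include placebo contrasts and unfavourable results that bear on no primary claim.

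**The trial is exploratory.** Protocol 13.2 and SAP 12.2 both say so, and both then commit to confirmatory principles with alpha control. The label does not remove the need for one defined primary test.

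**The benchmark is reconstructed.** K is not stated and the separate sample-size document is not available here. This stands, but K = 9 and K = 18 both give more than 80%.

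**Conclusion.** The point holds as an omission and a contradiction. SAP 12.2 leaves out the test that carries the protocol's alpha, multiplicity control and sample size, and the method it names is not the one SAP 8.2.1 and 9 describe. The 80% power and 5% error rate belong to Wei-Lachin (about 83–88% at 27–30 per arm).

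At correlation 0.4 and the 27 evaluable per arm that the 10% allowance implies, none of the readings examined gives both figures. Composites keep the error rate below 5% but have less than 80% power. Counting any scale reaches 80% but roughly doubles or triples the error rate. The nearest case is success on either of two composites under reading (b); it touches 80% only with all 30 per arm evaluable and placebo equal to CRB.

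The figures assume normal data, equal effects and correlations across scales and visits, and a simple-mean composite. The alpha readings are assumptions because the SAP states none. The contradiction depends on none of these.

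**What to change.** In SAP 12.2 and 13.4:

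- State one primary analysis: the Wei-Lachin test at one-sided 0.05 of rTMS + CRB against CRB + sham over the ensemble at both visits, ranking only those two arms.
- Name the sub-score used for each ensemble scale, since section 4 codes several per scale. Reconcile the Multitasking Test, which is a primary endpoint in SAP 8.1 but absent from the ensemble in SAP 9.
- Orient every component so that higher means better; times in seconds, error counts and Hamilton totals need reversing.
- Report the average and per-scale Mann-Whitney effects with confidence intervals.
- Test CRB against placebo the same way, as the secondary assay-sensitivity check.
- Label Kruskal-Wallis/Dunn exploratory. Define COMP1 and COMP2 or remove them.

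The cost is SAP wording and a short R or SAS routine, with no new data. Protocol 13.16 requires the SAP to be final before decoding, so the change belongs before then. Parts of the SAP (sections 3, 4 and 13.5) are in the past tense, so it is unclear whether the blind still held. If it has been broken, the protocol's test should still be reported as primary and the departure disclosed.
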